6.2. Subject Screening

After local ethics committee approval is obtained, consecutive subjects ≥ 75 years of age in whom revascularization by PCI of at least one coronary artery stenosis with visually assessed diameter stenosis $\geq 50\%$ is considered by interventional cardiologists participating in this trial will be identified and screened for study eligibility. Subjects eligible for enrollment per the general inclusion and exclusion criteria will be asked to sign an informed consent form for the SENIOR randomized trial. Subjects ≥ 75 years in the participating centers who do not satisfy inclusion and exclusion criteria but are treated by PCI during the same period will be documented on the patient log as well as the reason of non-inclusion.

6.3. Informed Consent

Prior to participation in the study, all eligible subjects must review, date and sign the Study Patient Informed Consent (PIC) form.

Eligible patients may only be included in the study after providing written (witnessed, where required by law or regulation), EC approved informed consent, or, if incapable, and if required by local law or regulation, after such consent has been provided by a legally acceptable representative of the patient. In the case of witnessed verbal consent, written informed consent should be obtained within 24 hours of procedure and must be obtained before discharge. Failure to obtain signed informed consent renders the patient ineligible for the study.

According to the European Directive 2001/20/EC of 4 April 2001, in emergency cases, a consent must be given by a patient's legal representative (if present); if the person concerned is unable to write, oral consent in the presence of at least one witness may be given in exceptional cases, as provided in national legislation. In this study, any verbal consent given by a patient in an emergency situation will be witnessed and documented. Written consent will be obtained as soon as the patient is able to provide written consent.

Any changes to the proposed consent form must be agreed to by the sponsor before

submission to the EC and a copy of the approved version must be provided to the CERC after EC approval.

The Investigator or designated member of the study site personnel must explain the study in detail, talking through all details described in the PIC. The patient must be given the opportunity to ask questions and ample time to consider his/her participation. If the patient is willing to participate in the study he/she or legal representative must sign and date two copies of the Informed Consent, which must be signed and dated at the same time, by the investigator or designee who explained the study. One copy of the PIC will be given to the patient and the other one will be retained in the study specific binder at the site. The process of obtaining informed consent should be documented in the patient source documents.

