Primary analytical population	The primary analysis of the composite endpoint of all-cause mortality, myocardial infarction, stroke and ischemia-driven target lesion revascularization will be performed on the intent-to-treat (ITT) population.
Statistical Method	The primary endpoint is a composite of all-cause mortality, myocardial infarction, stroke or ischemia-driven TLR with an

	
anticipated median follow-up of one year (efficacy).
 
The SENIOR study is powered to test the superiority of the Synergy[®] II with a relative 25% reduction of the primary endpoint
 
Assuming the following:
 
• primary endpoint event rate is 31% in control treatment arm at 1 year (interpolated from the most contemporary and accurate references)• minimum time to follow-up is 1 year• a constant dropout rate yielding 15% lost to follow-up at 1 year• two-sided alpha = 0.05• then a sample size population of 560 subjects per arm will provide 80% power to demonstrate superiority using a chi-square test comparing the event rates at 1 year from the Kaplan-Meier curves. The definitive total number will be 1.200 patients (600 in each arm).
--	--

1-Introduction

Coronary artery disease is a prevalent disease in patients ≥ 75 years with or without other risk factors. Aging of the population leads to frequent hospitalizations and significant medical and economic burden. However, there is currently no clear recommendation for how to treat specifically patients above 75 years suffering coronary artery disease (CAD). Patients above 75 years of age have been systematically underrepresented and highly selected in major clinical randomized trials underlying current recommendations for general population suffering stable or unstable CAD (1).

2-Background

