The primary objective of this study is to establish the efficacy and safety of the everolimus eluting stent (Synergy[®] II, Boston Scientific), in association with a reduced duration of dual antiplatelet therapy, (comparable to the one recommended when using a BMS) in patients ≥ 75 years by demonstrating that compared to BMS (Omega[®], Rebel[®], Boston Scientific), treatment of coronary stenosis with Synergy[®] II will result in lower rates of the composite events of all-cause mortality, myocardial infarction, stroke or ischemia driven target lesion revascularization at an anticipated median follow-up duration of one year.

4-Study design

4-1 Study design

A total of 1,200 subjects will be enrolled in this study. This study will be a prospective, single blinded, randomized multicenter trial at approximately 40 international centers. Following diagnostic angiography demonstrating significant CAD requiring PCI and if the subject meets all the study entry criteria, he/she will be eligible for the study and randomized to: a) PCI using the Synergy[®] II stent or b) PCI with BMS stent with dual antiplatelet therapy of similar duration for both groups. Follow-up for all randomized subjects will continue for 1 year.

4-2 Subject Follow Up

All randomized subjects will be followed for at least 1-year period after baseline procedure. All randomized subjects will have a follow-up by telephone contact or office visit as described below:

- 30 days(+/- 5 days) visit: office visit

-
- 180 (+/-2weeks): telephone contact or office visit
 - 1 year visit(+ 4 weeks): office visit
 - 2 years (+/-4 weeks) visit: telephone contact or office visit.

4-3 Treatment strategy

All subjects participating in this randomized trial will have informed consent obtained after diagnostic angiography and prior to randomization. "Ad hoc" PCI is permitted as far as written informed consent has been obtained prior to the procedure. If more than one target lesion will be treated, all lesions must receive the treatment stent that has been assigned as per randomization (Synergy[®] II or Omega[®]/Rebel[®]).

5-Endpoints

5-1 Primary end point

The primary endpoint of this trial is the composite measure of MACCEs: all-cause mortality, myocardial infarction, stroke and ischemia driven target lesion revascularization (by PCI or CABG) at an anticipated median follow-up duration of 1 year (with all randomized subjects having reached the one year follow-up).

5-2 Secondary end points

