- **Primary endpoints** at 30 days, 180 days and 2 years
- **All individual component of the primary endpoint** at 30 days, 180 days, 1 year, and 2 years:
 - Cardiac death
 - Myocardial Infarction (according to Third Universal Definition)
 - Stroke
 - Ischemia-driven target lesion revascularization (by PCI or CABG)

-All revascularization (ischemia-driven and non-ischemia driven) at 30 days, 180 days, 1 year and 2 years:

- all target lesion revascularization (TLR)

- all target vessel revascularization (TVR)

- all non target vessel revascularization (non TVR)

-complete revascularization at baseline procedure, anatomic and functional

-Net benefit at 30 days, 180 days, 1 year and 2 years: association of composite events (all-cause mortality, myocardial infarction, stroke, ischemia driven target lesion revascularization, and **major bleedings**).

-Major bleeding complications (type 2, 3 and 5 BARC definition) at 30 days, 180 days, 1 year and 2 years (6)

-Stent thrombosis according to the definition of definite and probable stent thrombosis according to ARC (symptomatic or asymptomatic) at 30 days, 180 days, 1 year and 2 years (5),

-QoL at 12 months and 24 months

-Depression scale at 12 months and 24 months

-Cost effectiveness at 12 months

6-Selection and withdrawal of the subjects

6-1 Subject population

Male and female subjects could be enrolled in the present study if they are 75 years old or older at the time of randomization. The randomized trial will enroll approximately 1,200 patients who need to meet ALL eligibility criteria and provide written informed consent prior to randomization. Each site should enroll a minimum of one randomized subject, and may not enroll more than a maximum of 120 randomized subjects.

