18.2 Investigator responsibilities

Study Investigators will ensure that all work and services they provide will be conducted in compliance with the standards of good clinical and research practice, i.e. ISO 14155.

The investigator will ensure that the study is conducted in compliance with the Clinical Investigation Plan and the Investigator's Agreement.

The Investigator will be responsible for the day to day conduct of the clinical investigation as well as for the safety and well-being of the human subjects involved in the clinical investigation.

The Investigator will have the resources to conduct the clinical investigation properly and obtain from the sponsor information which he judges essential about the device and be familiar with this information.

The Investigator must obtain written EC approval prior to including any subject in the study.

The Investigator will be provided by the Sponsor with a sample informed consent that may be modified to meet individual EC (or Institutional Review Board (IRB)) requirements. Any modifications of the informed consent document must be submitted to the Sponsor for approval prior to submission to the EC/IRB. The Investigator shall ensure that adequate information is given to the subject both in oral and written form, on the nature of the study. This information shall be easily understandable by the subject. This information shall include the aims, expected benefits for him/her and/or others, risks and inconveniences and an explanation of any alternative methods, and of possible consequences of any withdrawal from the study. Subjects shall be allowed sufficient time to decide whether or not they wish to participate. The subjects shall be informed that his/her participation in the clinical investigation is confidential. Subjects shall be made aware that the data relating to the study may be made available to third parties while maintaining anonymity. Subjects shall sign the informed consent form prior to their inclusion in the study. A copy of the approved informed consent form along with a copy of each subject's signed consent form will be maintained by each Investigator in a

designated clinical study administrative file. A copy of the signed consent form must be given to each subject.

CERC will provide centres with a sample informed consent document.

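### Section 6.3 allows randomisation and stenting on witnessed verbal consent, then makes a patient who never signs ineligible; early death can trigger this rule, and other sections do not allow the verbal route

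*Protocol*

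**What the plan says.** Section 6.3 opens by requiring eligible patients to sign before they take part, and allows inclusion only after written consent from the patient or a legally acceptable representative. It then adds a second route: "In the case of witnessed verbal consent, written informed consent should be obtained within 24 hours of procedure and must be obtained before discharge". The next sentence reads: "Failure to obtain signed informed consent renders the patient ineligible for the study". For emergencies it adds that verbal consent will be witnessed and documented, and: "Written consent will be obtained as soon as the patient is able to provide written consent".

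Section 6.4.4 counts a verbally consenting patient as enrolled on the terms of 6.3. Section 8 places randomisation before PCI and refers to 6.3 for how consent is signed. Section 6.4.1 lists signing among the inclusion criteria, and 6.4 requires every criterion to be met.

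Other places give a different order and mention no verbal exception:

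- Protocol Summary, Study design: the form is signed, then the patient is randomised.
- Section 4-3: ad hoc PCI is "permitted as far as written informed consent has been obtained prior to the procedure".
- Section 6-1: patients "need to meet ALL eligibility criteria and provide written informed consent prior to randomization".
- Section 18.2: "Subjects shall sign the informed consent form prior to their inclusion in the study".

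The Protocol Summary says the primary analysis "will be performed on the intent-to-treat (ITT) population".

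**The concern.** Eligibility should be settled before randomisation. On the verbal route it depends on a signature that falls due after the patient has been allocated and treated. A patient who dies first cannot supply it, and all-cause death is a component of the primary endpoint. A site or data manager who applies 6.3 as written could therefore set aside a randomised patient because of the outcome. That would remove an early event from an analysis meant to include everyone randomised.

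The trial is single-blind and the operator implants the allocated stent, so the protocol offers no assurance that such losses would fall evenly between the arms. Separately, a site cannot follow both consent orders. Under one reading, every patient who enters on verbal consent is a protocol violation.

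**Working it through.** **Sequence on the verbal route.**

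1. Witnessed verbal consent is accepted (6.3) and suffices for enrolment (6.4.4).
2. Randomisation takes place before PCI (Section 8).
3. PCI follows. The signature is a target within 24 hours and a requirement before discharge (6.3).
4. Without a signature the patient is ineligible (6.3), and also fails an inclusion criterion (6.4.1).

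Step 4 comes after randomisation and treatment. Death between steps 2 and 3, or between PCI and signature, makes the condition impossible to meet.

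**Does another section cover this patient?**

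- Section 10.3 covers withdrawal before randomisation, discontinuation before PCI, and withdrawal of consent once PCI has begun. The last calls for a final visit. None describes a patient who dies with consent incomplete.
- Section 10.4 keeps patients given non-study stents or procedures for ITT. No matching sentence exists for unsigned patients.
- Section 13.2 collects endpoint events in subjects who received a study stent. It does not say whether a patient declared ineligible is still a subject.
- The Protocol Summary names ITT as the primary population but does not define it.

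**Size.** The number lost would be 1,200 × (share of emergency patients) × (share of these entering on verbal consent) × (share dying unsigned). The protocol gives none of the three shares, so no estimate is possible. The following only shows direction. It assumes 3, 6 or 12 lost patients per affected arm of 600 (0.5%, 1% or 2%), each with a primary event.

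*No true effect, loss from one arm only.* Control events: 600 × 0.31 = 186. After losing k events the risk is (186 − k)/(600 − k).

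| k | Risk | Risk ratio against 0.31 | Difference (points) |
|---|---|---|---|
| 3 | 183/597 = 0.3065 | 0.989 | 0.35 |
| 6 | 180/594 = 0.3030 | 0.978 | 0.70 |
| 12 | 174/588 = 0.2959 | 0.955 | 1.41 |

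*Design effect (31% against 0.75 × 31% = 23.25%), equal loss of share x from both arms.* Each risk becomes (p − x)/(1 − x).

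- x = 0.005: 30.65% and 22.86%; ratio 0.2275/0.305 = 0.746.
- x = 0.02: 29.59% and 21.68%; ratio 0.2125/0.29 = 0.733.

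The design ratio is 0.75, so equal loss moves it only slightly.

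**Sample size.** The planned figure does not depend on this point. For 31% against 23.25%, two-sided 0.05 and 80% power, the two-proportion formula gives 516 per arm. Constant dropout reaching 15% at one year costs about 7.5% of exposure on average, and 516/0.925 = 558, close to the stated 560. A simulation of 10,000 trials comparing one-year Kaplan-Meier rates gave 80.6% power at 560 per arm.

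**The case against.** The strongest reply is that Section 6.3 calls the unsigned patient ineligible but nowhere says that patient leaves the analysis set. Sections 10.3 and 10.4 lean towards keeping data, and Section 12 defers the analyses to a statistical analysis plan, not available here, which may define ITT to include everyone randomised. This is right as far as it goes: removal from ITT is something a reader might infer, not something the protocol states. But a statistical analysis plan cannot reconcile consent instructions, or recover data that sites stopped collecting because they took a patient to be out of the study.

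Other tempting extensions do not hold:

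- **Loss of capacity.** Section 6.3 lets a legal representative sign, so incapacity does not by itself make a patient ineligible.
- **Refusal after stenting.** This is arguably withdrawal once PCI has begun, which 10.3 handles, although 10.3 does not mention a patient who never signed.
- **Section 8.** It defers to 6.3 and so is not a clear contradiction.
- **Deadlines within 6.3.** A 24-hour target, a limit at discharge and a duty to obtain the signature as soon as the patient can give it are compatible.
- **Bias by arm.** The Background reports a stent-thrombosis difference by 30 days for cobalt-chromium everolimus stents. It says nothing about the short interval before signing, and uneven pursuit of signatures is only a possibility.

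Requiring a signature is also an ethical and legal safeguard, and national law may forbid use of an unsigned patient's data whatever the protocol says. That limits the remedy but does not remove the need to state the rule.

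**Conclusion.** The point holds in a limited form. Followed literally, the protocol makes eligibility depend on an event after randomisation that early death can prevent, and it does not say how such a patient is analysed. The consent order is contradictory: 6.3 and 6.4.4 permit what the Protocol Summary, 4-3 (for ad hoc PCI), 6-1, 18.2 and the opening of 6.3 do not.

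It would go too far to say that the protocol removes these patients from ITT, or that a known share of events is lost. The number is probably small, because death before signing on the verbal route should be uncommon, but the documents give nothing from which to calculate it. The illustrative figures rest wholly on the assumed counts. Sample size and power stand as planned.

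**What to change.** Reconcile the Protocol Summary and Sections 4-3, 6-1, 6.3, 6.4.4 and 18.2 to one consent order, and check that 6.4.1 and 8 agree with it. Either remove the verbal route from 6.3 and 6.4.4, or state it as an exception wherever written consent is required first.

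If the verbal route is kept:

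- limit the ineligibility rule to patients not yet randomised;
- state that a patient randomised under documented, witnessed consent who dies before signing stays in the ITT population, with data retained as local law permits;
- say in 10.3 that a later refusal to sign is handled as withdrawal of consent;
- report randomised patients without a signature by arm.

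The cost is a wording amendment and its ethics submission, with no added visits, procedures or patients. The drawback is that some countries may not allow an unsigned patient's data to be kept; those patients can then only be counted by arm.

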6.4. Eligibility Criteria

Subjects must meet **ALL** of the inclusion criteria to be considered for the randomized clinical trial. If **ANY** of the exclusion criteria are met, the subject cannot be included in the randomized clinical trial.

6.4.1. Inclusion Criteria

All subjects participating in the clinical trial will have informed consent obtained prior to randomization.

Inclusion Criteria (ALL must be present):

- Patient \geq 75 years old
- One or more significant coronary artery stenosis (defined as \geq 70% by visual assessment or \geq 50% with Fractional Flow Reserve $<$ 0.80) or a left main coronary stenosis \geq 50% by visual assessment) suitable for PCI with one of the following present:

-Silent ischemia,

-stress-induced myocardial ischemia \geq 10% of myocardium in a asymptomatic

patient

or

-stress-induced myocardial ischemia < 10% of myocardium in an asymptomatic patient AND FFR \leq 0.80

or

-**Stable angina**, in a patient with objective ischemia despite optimal medical therapy

or

-acute coronary syndrome including: unstable angina, non ST- and ST elevation myocardial infarction.

-All patients must also sign informed consent as per local law and comply with all study process during follow up for at least one year.

6.4.2. Exclusion Criteria

The subject is not eligible for the study if **ANY** of the following is present:

- Indication for myocardial revascularization by coronary artery bypass grafting,
- Subjects unable to tolerate, obtain or comply with dual antiplatelet therapy for at least six month (acute coronary syndrome) or at least one month (stable angina or silent ischemia),
- Subjects requiring additional surgery (cardiac or non-cardiac) within one month,
- Non cardiac co-morbidities with life expectancy less than 1 year,
- Prior hemorrhagic stroke,
- Known allergy to aspirin or P2Y₁₂ inhibitors,
- At least one contra indication to all the authorized P2Y₁₂ inhibitors at the requested dose (in case of contra indication to only one of two of the P2Y₁₂ inhibitors, the investigators are

allowed to use the P2Y₁₂ inhibitors for which no allergy is known).

-Silent ischemia < 10% of the myocardium with FFR ≥ 0.80.

-Participation in another clinical trial

6.4.3. Patients with atrial fibrillation requiring chronic anticoagulation

Patients with atrial fibrillation could participate to the study precluding that they meet all inclusion criteria and none of the exclusion criteria. In addition to their chronic anticoagulation, they will receive clopidogrel as the only accepted ADP P2Y₁₂ receptors inhibitors. Clopidogrel loading dose will be 300/600mg according to physician discretion. DAPT will be maintained for one month for all patients. After one month, aspirin will be stopped, and only clopidogrel will be maintained.

6.4.4. Patients enrollment

The patient is enrolled in the study when he/she has signed the informed consent (verbal consent is only acceptable as above), has a lesion that is treatable with a study stent, is randomized either through the eCRF and receives a study treatment assignment.

7-Baseline assessment

At inclusion into this study, routine examinations, if performed, will be captured: physical examination, including height and weight, heart rate and blood pressure and relevant medical history including detailed evaluation of bleeding risk and lesion characteristics as well as:

-Angina Status

-Routine Laboratory Tests including CK and/or CK-MB or troponin prior to the procedure (when available)

-12 Lead electrocardiogram

-The following questionnaires

- Geriatric Depression Scale
- EuroQoL-5D 5L questionnaire

8-Randomization procedure

Randomization will occur prior to PCI but after all eligibility criteria for the study have been met, including that a treatable lesion has been identified and informed consent has been signed according to section 6.3. Patients will be randomized using a eCRF. The type of ADP P2Y₁₂ inhibitor and the planned duration of DAPT will be determined before the randomization process.

Randomization will be stratified by the choice of ADP P2Y₁₂ and by center.

9-Treatment of the subjects

9.1 Percutaneous coronary interventions.

After randomization, the patients will undergo PCI with the randomized stent Synergy[®] II or Omega[®]/Rebel[®] stent . Transradial 6F approaches are strongly recommended. The choice of guiding catheters, guidewires, predilatation, atherectomy devices, post dilatation and intra coronary imaging system (IVUS, OCT) is let to the investigators discretion. The available DES and BMS exist in different sizes and length.

-everolimus eluting stents (Synergy[®] II stents):

2.25 mm x 8, 12, 20, 28, 32, 38 mm

2.50 mm x 8, 12, 20, 28, 38 mm

3.00 mm x 8, 12, 20, 28, 38 mm

3.50 mm x 8, 12, 20, 28, 38 mm

4.00 mm x 8, 12, 20, 28, 38 mm

-bare metal stents (Omega[®] or Rebel[®] stent)

2.25 mm x 8, 12, 20, 28, 32, 38 mm

2.50 mm x 8, 12, 20, 28, 38 mm

3.00 mm x 8, 12, 20, 28, 38 mm

3.50 mm x 8, 12, 20, 28, 38 mm

4.00 mm x 8, 12, 20, 28, 38 mm

9.2. Adjunctive Treatment.

Antithrombotic regimen within the cathlab, including unfractionated heparin, low molecular weight heparin, bivalirudin, fondaparinux, is left to the physician discretion. GpIIb / IIIa inhibitors can be used in selected cases in patients with STEMI but are not recommended for stable patients or for patients with silent ischemia.

-Dual antiplatelet therapy will be administered for **similar duration** after Synergy[®] II and Omega[®]/Rebel[®] stent or any other BMS available implantation. DAPT duration will be one month after PCI for stable angina and silent ischemia, and six months after PCI for acute coronary syndroms, **irrespective of the type of stent** (Synergy[®] II or Omega[®]/Rebel[®] stent).

-Aspirin will be prescribed to all patients at an initial intra venous or oral loading dose of 150-300mg and at a maintenance dose of 75-100 mg orally daily, indefinitely (except in patients with chronic anticoagulation). For patients not already on P2Y₁₂ inhibitors they will be added to aspirin before or immediately after percutaneous coronary intervention and maintained over one month (stable angina or silent ischemia) or 6 months (ACS).

-All patients in the trial will be treated by either:

-clopidogrel 600mg loading dose and 150mg/d or 75mg/d

OR

-prasugrel 60mg loading dose and 5 mg/d orally

OR

-ticagrelor 180mg loading dose and 90mg/bd orally

over one month after PCI. The P2Y₁₂ inhibitor will be prolonged over 6 months only in patients with acute coronary syndrome, irrespective of the type of the stent.

Optimal medical treatment.

Anti ischemic treatment should be added to medical treatment and include beta blocker agents in patients without contra indication.

Calcium channel blocking agents can replace beta blocker agents in patients with contra indications to these agents.

A proton pump inhibitor (PPI) is strongly recommended according to physician discretion (pantaprazole 20mg, ezoprazol 20mg, lanzoprazole 20mg, rabeprazole 20mg or omeprazole 20mg).

10-Follow-up visits

Every effort should be made for collecting the subject data thanks to an on-site visit or telephone contact, as described below:

- 30 days(+/- 5 days) visit: office visit

-
- 180 (+/-2 weeks): telephone contact or office visit
 - 1 year visit (+ 4 weeks): office visit
 - 2 years (+/-4 weeks) visit: telephone contact or office visit.

These visits will include information regarding angina status, any adverse events including MACCEs and bleeding events, concomitant cardiovascular and other important medication use and any hospitalizations including any interventional treatment that occurred since the previous contact. If available the ECG results will be collected at each follow-up visit.

The following questionnaires

- Geriatric Depression Scale
- EuroQoL-5D questionnaire

will be collected at 12 months and 24 months.

If the patient cannot be contacted, information from the patient's identified point of alternative contact will be utilized.

